6. OBJECTIVES AND ENDPOINTS

Table 5: Objectives and Endpoints

Objectives	Endpoints		
Primary	Ŷ		
To evaluate the long-term safety and pharmacodynamic (PD) effects of ACE-083 in patients with facioscapulohumeral muscular dystrophy (FSHD) previously enrolled in study A083-02 and in patients with Charcot Marie Tooth (CMT) disease types 1 and X (CMT1 and CMTX) previously enrolled in study A083-03.	 Presence and nature of adverse events (AE) including injection site reactions and changes in clinical laboratory parameters Percent change from baseline in muscle volume of injected muscle by magnetic resonance imaging (MRI) 		
Secondary			
 To evaluate safety and PD effects of every 4 week (q4w) dosing in the loading phase, and of q4w and q8w dosing in the maintenance phase. To evaluate changes in strength, motor function, and quality of life (patient-reported outcomes) during the maintenance and loading phases of treatment. To evaluate the PK of ACE-083 when administered as a local muscle injection during the maintenance and loading phases of treatment. To evaluate safety and PD effects of every 4 week (q4w) dosing in the loading phase, and of q4w and q8w dosing in the maintenance phase. 	 Percent and absolute change from baseline in the intramuscular fat fraction of injected muscle by MRI Percent change from baseline in strength measurements Percent and absolute change from baseline in functional assessments: For tibialis anterior (TA) muscle: 10-meter walk/run, 6-minute walk test, 4-stair climb (subjects from A083-02 only), and 100-meter timed test; for biceps brachii (BB) muscle, mid-level and high level performance of the upper limb (PUL) test Absolute change from baseline in FSHD-health index (FSHD-HI, subjects from A083-02) or CMT health index (CMT-HI, subjects from A083-03) total score and subscale scores PK parameters for ACE-083 serum concentrations over time 		
Exploratory			
 To evaluate changes in biomarkers To evaluate ACE-083 PK/PD relationships. 	 Percent and absolute change from baseline in biomarkers Percent and absolute change in PD parameters as a function of ACE-083 exposure. 		

7. STUDY DESIGN

7.1. Overview of Study Design

This is an open-label, multicenter, phase 2 extension study to evaluate the safety, tolerability, PD, efficacy, and PK of ACE-083 in patients with FSHD previously enrolled in Study A083-02 and patients with CMT1 and CMTX previously enrolled in Study A083-03. This study will be conducted in two Parts: Part 1, consisting of a loading phase of 6 months, and Part 2, consisting of a maintenance phase of 24 months. Subjects who enroll in this study without interruption of treatment following the previous study will enroll directly into Part 2 of this study.

Part 1 is a non-randomized, open-label, loading phase in which subjects will receive bilateral injections of 240 mg/muscle ACE-083 every 4 weeks. Part 1 will include subjects previously treated in Part 1 of Studies A083-02 and A083-03 after a washout period of at least 3 months. Upon completion of this 6-month loading phase, these subjects will then rollover into Part 2 of this study, which is the maintenance phase.

Subjects who complete Part 2 of study A083-02 or A083-03 will enroll directly into Part 2 of this study without interruption. The end-of-treatment visit in the previous study will coincide with the Day 1 visit of this study. Part 2 is an open-label maintenance phase study in which subjects will be randomized to receive bilateral injections of 240 mg/muscle ACE-083 either every 4 weeks or every 8 weeks. A schematic diagram of subject enrollment and disposition is shown in Figure 1.

Duration of Treatment

For subjects enrolled in Part 1 and Part 2 of this study, study duration will be approximately 33 months, including a screening period of up to 1 month, the 6-month Part 1 loading phase, the Part 2 maintenance phase of 24 months, and a 2-month follow-up period.

For subjects who enroll directly into Part 2 of this study from Part 2 of Study A083-02 or A083-03, study duration will be approximately 26 months, including a maintenance phase of 24 months and a 2-month follow-up period. These subjects will sign the Informed Consent Form (ICF) for this study at the end-of-treatment visit for Study A083-02 or Study A083-03 (i.e., Day 1 of this study).

If a subject has a positive anti-drug antibody (ADA) result at the last scheduled follow-up visit, the subject may be asked to return for additional ADA testing approximately every 3 months, until a negative result is obtained or the titer is no longer increasing.

Part 1 (non-randomized, open-label, loading phase with subjects from A083-02 Part 1 and A083-03 part 1)

Part 1 will consist of 3 cohorts of up to 18 subjects each. In this loading phase, 240 mg/muscle ACE-083 will be administered bilaterally q4w for 6 doses (6 months) into either the TA muscle or BB muscle, depending on the muscle injected in the previous study; subjects may not switch muscle cohort upon enrollment in this study. Subjects in each cohort will be enrolled in a screening period of up to 4 weeks before beginning treatment.

Subjects enrolled in Cohorts 1a and 1b will have completed the 3-month, dose escalation, non-randomized, open-label Part 1 of Study A083-02. As part of that study, these subjects will have

Revision: 00 previously received injections of up to 240 mg/muscle ACE-083, either unilaterally or bilaterally, q3w for up to 5 doses.

Subjects enrolled in Cohort 1c, will have completed the 3-month, dose escalation, non-randomized, open-label Part 1 of Study A083-03. These subjects will have previously received up to 240 mg/muscle ACE-083 bilaterally by injection into the TA every q3w for up to 5 doses.

Part 2 (randomized, open-label rollover maintenance phase, with subjects from Part 1 A083-04 and A083-02 part 2 and A083-03 part 2)

Part 2 will consist of 6 additional cohorts. Cohorts 2a, 2b, and 2c will receive 240 mg/muscle ACE-083 q4w, and Cohorts 3a, 3b, and 3c will receive 240 mg/muscle ACE-083 q8w. Cohorts are separated and randomized based upon disease (FSHD or CMT) and target muscle (BB or TA).

Subjects who complete Part 1 (loading phase), will immediately rollover into Part 2 (open-label maintenance phase) treatment with ACE-083. The subjects will be randomized into treatment groups to receive 240 mg/muscle ACE-083 bilaterally either q4w or q8w.

Subjects who completed Part 2 of Study A083-02 or Part 2 of Study A083-03 will directly enter into Part 2 (open-label maintenance phase) of this study and will be randomized to receive 240 mg/muscle either q4w or q8w. The first study visit of this study will coincide with the end-of-treatment visit of the previous study (either A083-02 or A083-03).

7.2. Justification for Dose Level

A starting dose of 150 mg/muscle was used in the dose escalation cohorts in Part 1 of Phase 2 Study A083-02 and Part 1 of Phase 2 Study A083-03, with a maximum dose in these studies of 240 mg/muscle unilaterally or bilaterally q3w for 3 months (5 doses). All doses were well-tolerated, including bilateral cohorts. The most common TEAEs in all cohorts were grade 1 injection site reactions, and there were no treatment-related SAEs. Injections of 150 to 240 mg/muscle ACE-083 produced significant, dose-dependent muscle volume increases that were maintained for up to 8 weeks following the last dose.

Based upon these safety and efficacy data, the dose of 240 mg/muscle bilaterally was chosen for Part 2 of the A083-02 and A083-03 studies as well as for this extension study. This study will evaluate if long-term, maintenance phase dosing of 240 mg/muscle q8w and/or q4w can maintain total muscle volume increases and functional improvements reached at the conclusion of the loading phase (q3w or q4w for 6 months). Any changes in the dose level or schedule in this study will be determined following review of study data and recommendations from the SRT. A maximum absolute dose level of 240 mg/muscle has been chosen based in part on administration feasibility and volume constraints.

7.3. Benefit/Risk Assessment

Information about the known and expected benefits, risks, SAEs, and reasonably anticipated AEs of ACE-083 is provided in the IB.

8. STUDY POPULATION

8.1. Inclusion Criteria

Subjects are eligible to be included in the study only if they meet all of the following criteria at screening:

Inclusion Criteria:

- 1. Completion of treatment with study drug per protocol and completion of the end of treatment (ET) visit in Study A083-02 or Study A083-03.
- 2. Females of childbearing potential (defined as sexually mature women who have not undergone hysterectomy or bilateral oophorectomy, or are not naturally postmenopausal ≥ 24 consecutive months) must have negative urine pregnancy test prior to enrollment and use highly effective birth control methods (abstinence, oral contraceptives, barrier method with spermicide, or surgical sterilization) during study participation and for 8 weeks following the last dose of ACE-083. Hormonal birth control use must be stable for at least 14 days prior to Day 1. Males must agree to use a condom during any sexual contact with females of childbearing potential while participating in the study and for 8 weeks following the last dose of ACE-083, even if they have undergone a vasectomy. Subjects must be counseled about contraception prior to the first dose of ACE-083 and every three months thereafter during the study.
- 3. Ability to adhere to the study visit schedule/procedures and to understand and comply with protocol requirements
- 4. Signed written informed consent

8.2. Exclusion Criteria

Subjects will be excluded from study enrollment if they meet any of the following criteria at screening:

- 1. Current/active malignancy (e.g., remission less than 5 years' duration), with the exception of fully excised or treated basal cell carcinoma, cervical carcinoma in-situ, or ≤ 2 squamous cell carcinomas of the skin
- 2. Co-morbidities, including symptomatic cardiopulmonary disease, significant orthopedic or neuropathic pain, or other conditions that, in the opinion of the investigator, would limit a subject's ability to complete strength and/or functional assessments
- 3. Type 1 or type 2 diabetes mellitus
- 4. Thyroid disorder unless condition is stable with no change in treatment for at least 4 weeks before the first dose and no expected change for duration of study
- 5. Renal impairment (serum creatinine ≥ 2 times the upper limit of normal [ULN])
- 6. Aspartate transaminase (AST) and/or alanine transaminase (ALT) \geq 3 times ULN
- 7. Increased risk of bleeding (i.e., due to hemophilia, platelet disorders, or use of any anticoagulation/platelet modifying therapies up to 2 weeks prior to Study Day 1 and for duration of study; single agent low dose aspirin [≤ 100 mg daily] is permitted)

- 8. Severe deformity or ankle fixation that would sufficiently limit passive range of motion to affect functional assessments (TA patients only)
- 9. Major surgery within 4 weeks prior to Study Day 1
- 10. Chronic pharmacologic doses of systemic corticosteroids (≥ 2 weeks) within 4 weeks before Study Day 1 and for duration of study; intra-articular/topical/inhaled/intranasal physiologic doses of systemic corticosteroids are permitted
- 11. Androgens, growth hormone, insulin or oral hormone replacement therapy within 6 months before Study Day 1 and for duration of study; topical physiologic androgen replacement is permitted
- 12. Any change in medications potentially affecting muscle strength or function within 4 weeks of Study Day 1 and for duration of study (e.g., creatinine, CoQ10, systemic beta-adrenergic agonists)
- 13. Previous exposure to any other investigational agent (not including ACE-083) potentially affecting muscle volume, muscle strength, or muscle or nerve function within 5 half-lives of last dose plus an additional 8-week washout period (or 12 weeks prior to Study Day 1 if half-life is unknown)
- 14. Significant change in physical activity or exercise (e.g., significant increase or decrease in intensity or frequency) within 8 weeks before Study Day 1 or inability to maintain the baseline level of physical activity throughout the study
- 15. Any condition that would prevent MRI scanning or compromise the ability to obtain a clear and interpretable scan of the treated muscles (e.g., knee/hip replacement metallic implants)
- 16. Known active substance abuse, including alcohol
- 17. History of sensitivity to protein pharmaceuticals
- 18. Female that is pregnant or lactating/breast-feeding

8.3. Screen Failures

Individuals who do not meet the criteria for participation in this study (screen failure) may be rescreened up to 2 additional times. The interval between re-screenings should be at least 4 weeks after the end of the 4-week screening period (i.e., the earliest re-consent may occur is 8 weeks after the prior consent was signed). Each time a rescreening is performed, the individual must sign a new ICF. If a test is repeated within the screening window, the patient does not need to sign a new ICF.

Study A083-04 Revision: 00

9. DISCONTINUATION / WITHDRAWAL CRITERIA

The reasons for treatment discontinuation / study withdrawal must be recorded in the patient's case report form (CRF). The investigator must notify the sponsor and medical monitor when a patient has been withdrawn from the study.

All patients who are withdrawn from the study prior to the end of treatment (EOT) visit should complete the tests and evaluations (excluding the MRI if it has been done within 4 weeks of study withdrawal) scheduled for the EOT visit (Day 673) at the time of withdrawal and will be asked to return to the clinic to complete the remaining follow-up visit assessment.

9.1. Discontinuation of Study Treatment

Reasons that may lead to discontinuation of study treatment include:

- Treatment completed
- Adverse event
- Patient request (withdrawal of consent)
- Death
- Lost to follow-up
- Pregnancy
- Protocol deviation
- Study terminated by sponsor¹

9.2. Withdrawal from the Study

Reasons that may lead to a patient's withdrawal from the study include:

- Study terminated by sponsor¹
- Patient's request
- Screen failure
- Patient's unwillingness or inability to comply with the protocol
- Death
- Lost to follow-up
- Adverse event

¹ The sponsor may terminate this study after consultation with the investigator and the SRT at any time for safety or administrative reasons. The sponsor will terminate the study if the occurrence of SAEs or other findings suggests unacceptable risk to the health of the patients.

Clinical Study Protocol Study A083-04

ACE-083

Revision: 00

Lost to Follow Up 9.3.

A subject will be considered lost to follow-up if he or she repeatedly fails to return for scheduled visits and is unable to be contacted after three attempts by the study site. Every attempt should be made to collect all data on discontinued patients.

Clinical Study Protocol Study A083-04

Revision: 00

10. TREATMENT OF SUBJECTS

10.1. Treatments Administered

Using electromyography (EMG) or ultrasound guidance, each dose of study drug will be administered into the non-tendinous portion of the target muscle (TA or BB) as a series of up to 4 equal-volume injections. The use of EMG or ultrasound guidance will help to ensure that viable muscle is present at the injection site. If the degree of atrophy or fibro-fatty infiltration poses administration challenges, injections of ACE-083 should be distributed approximately 2 cm apart into viable muscle. Injection site locations as well as measures to avoid adjacent nerves and blood vessels, and prevent intravascular injection are outlined in the IP Handling Guide.

For Part 1 of this study, the dose and schedule will be 240 mg/muscle administered bilaterally by injection into the TA or BB muscles every 4 weeks for up to 6 doses.

For Part 2, ACE-083 will be administered q4w for up to 24 months (24 doses) or q8w for up to 24 months (12 doses). Subjects who complete the Phase 1 loading phase treatment period will immediately be randomized into the 24-month maintenance phase. The planned dose schemes for Parts 1 and 2 are shown in Table 6 and Table 7.

Table 6: Part 1: Loading Phase; N=Up to 54; ACE-083 240 mg/muscle bilaterally q4w

Cohort	Disease	Muscle	N
1a	FSHD	Tibialis anterior (TA)	Up to 18
1b	FSHD	Biceps brachii (BB)	Up to 18
1c	CMT	Tibialis anterior (TA)	Up to 18

Table 7: Part 2: Maintenance Phase; N=Up to 150; ACE-083 240 mg/muscle bilaterally

Cohort	Disease	Muscle	Dose Interval	N
2a	FSHD	TA	q4w	Up to 23
2b	FSHD	BB	q4w	Up to 23
2c	СМТ	TA	q4w	Up to 29
3a	FSHD	TA	q8w	Up to 23
3b	FSHD	BB	q8w	Up to 23
3c	СМТ	TA	q8w	Up to 29

Study A083-04 Revision: 00

10.1.1. Individual Dose Modification Rules

For an adverse event (AE, including injection site reaction) of grade 3 or higher, regardless of relationship to study drug, treatment will be paused and the patient will be monitored weekly. At the discretion of the investigator, dosing may resume upon resolution of the AE to ≤ grade 1 or baseline and dose may be reduced. Dose delay and/or modification may be considered and implemented unilaterally or bilaterally. Up to two dose reductions are permitted: from 240 mg/muscle to 200 mg/muscle and from 200 mg/muscle to 150 mg/muscle. Dose will not be reduced below 150 mg/muscle. A maximum of 3 dose delays are allowed for subjects receiving q4w injections of ACE-083; only one dose delay is permitted for subjects in the q8w arm of Part 2 of the study.

10.2. Safety Review Team

An SRT, comprised at minimum of a principal investigator, medical monitor, and an independent neuromuscular specialist, will meet periodically (approximately every 3 months for the first six months, every six months thereafter) to review safety for each cohort. The reviews will include all collected safety data and will begin when at least 10 subjects have received at least 3 doses of ACE-083. The SRT will review safety data, including AEs, laboratory results, and vital signs, to assess overall safety. The SRT may request review of additional data including PD and efficacy measurements.

Based on review of relevant data, the SRT will make one or more of the following recommendations:

- Continue ACE-083 administration at the current dose
- Reduce the dose for all subjects within a cohort, or for the study as a whole
- Discontinue one or more cohorts, or the study as a whole

Any changes in the dose level or schedule (e.g., continued treatment with q4w or q8w) in this study will be determined following review of study data and recommendations from the SRT. Further details on the role of the SRT are included in the SRT Guidelines.

10.3. Concomitant Medications

During screening and throughout the study, subjects may take stable doses of medications for chronic conditions that are not specifically excluded by the protocol. These medications include: single agent low dose aspirin (≤ 100 mg daily), intra-articular/topical/inhaled/intranasal physiologic doses of corticosteroids, and topical physiologic androgen replacement. Any change in medications potentially affecting muscle strength or function (e.g., creatinine, CoQ10, or systemic beta adrenergic agonist) is not allowed. If there is an immediate clinical need during the study to prescribe a new medication or a new dosage of an existing medication for either a new or chronic condition, concurrent therapy may be administered at the discretion of the investigator. The investigator may consult the medical monitor regarding what constitutes a stable dose or a chronic condition. Information regarding concomitant medications will be collected beginning at study screening and will include all medications taken within 4 weeks prior to Study Day 1.

Subjects are not permitted to take the following: anticoagulation/platelet modifying therapies, systemic corticosteroids, systemic androgens, growth hormone, insulin, or estrogen ± progesterone hormone replacement therapy. Additionally, patients must be withdrawn from study treatment if at any time during their participation they receive other investigational compound(s) or start any new experimental or approved therapies related to the treatment of CMT or FSHD. This withdrawal excludes standard of care procedures and participation in observational research.

10.4. Treatment Compliance

Each dose of study drug will be administered via injections at the clinical site by the study staff and will be documented in the study record. Monitoring for patient compliance with the treatment regimen is therefore unnecessary.

10.5. Randomization and Blinding

Part 1: This is an open-label extension study enrolling subjects from Study A083-02 part 1 and Study A083-03 part 1 and does not require randomization.

Part 2: Subjects who have signed the informed consent and meet all eligibility criteria will be grouped by disease (FSHD or CMT) and target muscle (for FSHD; BB or TA) and then randomized to receive 240 mg/muscle bilateral ACE-083 either q4w or q8w. The randomization scheme will be computer-generated and will be prepared by a statistical group designated by the sponsor.

Because this study is an open-label extension of Studies A083-02 and A083-03, no blinding is necessary. Subjects will retain the unique identifying number assigned to them in the previous study.

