Subjects who complete Part 1 of this study (the loading phase), Part 2 of A083-02, or Part 2 of A083-03 will enroll directly into the Part 2 open-label maintenance phase of treatment with ACE-083. These subjects will be randomized (1:1) to receive ACE-083, 240 mg/muscle bilaterally, either q4w or q8w.

Number of Subjects (planned)

Up to 54 subjects from Study A083-02 Part 1 and Study A083-03 Part 1 will be enrolled in Part 1 of the study. A total of up to 150 subjects will be enrolled in Part 2 of the study; Part 2 will be comprised of up to 54 subjects from Part 1 of this study, up to 56 subjects from Part 2 of Study A083-02, and up to 40 subjects from Part 2 of Study A083-03. Total study enrollment will be up to 150 subjects.

Diagnosis and Main Criteria for Eligibility

Inclusion Criteria:

- 1. Completion of treatment with study drug per protocol and completion of the end of treatment (ET) visit in Study A083-02 or Study A083-03
- 2. Females of childbearing potential (defined as sexually mature women who have not undergone hysterectomy or bilateral oophorectomy or are not naturally postmenopausal ≥ 24 consecutive months) must have a negative urine pregnancy test prior to enrollment and use highly effective birth control methods (abstinence, oral contraceptives, barrier method with spermicide, or surgical sterilization) during study participation and for 8 weeks following the last dose of ACE-083. Hormonal birth control use must be stable for at least 14 days prior to Day 1. Males must agree to use a condom during any sexual contact with females of childbearing potential while participating in the study and for 8

weeks following the last dose of ACE-083, even if they have undergone a vasectomy. Subjects must be counseled about contraception prior to the first dose of ACE-083 and every three months thereafter during the study.

- 3. Ability to adhere to the study visit schedule/procedures and to understand and comply with protocol requirements
- 4. Signed written informed consent

Exclusion Criteria:

- 1. Current/active malignancy (e.g., remission less than 5 years' duration), with the exception of fully excised or treated basal cell carcinoma, cervical carcinoma in-situ, or ≤ 2 squamous cell carcinomas of the skin

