Safety: Unless otherwise specified, safety data will be summarized, by cohort and overall, using descriptive statistics; individual safety data will be listed. AEs will be coded using the current version of the Medical Dictionary for Regulatory Activities and incidence of treatment-emergent AEs will be presented by system organ class and preferred term. AE incidence rates will be described by cohort with and without regard to causality. The frequency of occurrence of overall toxicity, categorized by toxicity grades (NCI-CTCAE, current version), will be summarized. Change from baseline in clinical laboratory parameters, ECG, and vital signs will be summarized across time. Shift tables will be presented for selected laboratory parameters and vital signs. Physical examination results will be presented in listings.

Pharmacodynamics: Individual PD data (e.g., total muscle volume, contractile muscle volume, intramuscular fat fraction, and biomarker data) will be listed. For individual PD data that are measured bilaterally (e.g., MRI), the average of the left and right side assessments will also be listed and summarized. Descriptive statistics (raw data and change from baseline [percent and

absolute change]) will be provided by cohort and scheduled time where baseline is defined to be the last non-missing assessment done prior to first dose.

For total muscle volume, contractile muscle volume, and intramuscular fat fraction, a mixed model will be fitted to the data and the least squares estimate of the mean difference in the percent change from baseline at 6 months post first dose under the q4w regimen of ACE-083 versus placebo will be determined for each cohort with the corresponding 90% confidence interval, where placebo refers to data from the double-blind component of Part 2 of either study A083-02 or A083-03. This will be compared with the findings from Part 2 of studies A083-02 and A083-03 for the mean difference in the percent change from baseline under the q3w regimen vs placebo.

For biomarker data (e.g. CTX), raw data and changes from baseline (percent and absolute change) will be summarized by cohort and scheduled time.

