14.2.4. Pharmacodynamic Data

The primary analysis population for pharmacodynamic data will be the Per Protocol Set. The secondary analysis population will be the Full Analysis Set.

Pharmacodynamic parameters consist of the following:

- Muscle assessments: Muscle volume and intramuscular fat fraction of TA or BB by MRI
- Biomarkers: including, but not limited to, serum C-terminal collagen crosslinks (CTX)

Part 1

Individual pharmacodynamic data (e.g., total muscle volume, contractile muscle volume, intramuscular fat fraction, and biomarker data) will be listed. For individual pharmacodynamic data that are measured on the left and right side, the average of the left and right side assessments will also be listed and summarized. Descriptive statistics (raw data and change from baseline [percent and absolute change]) will be provided by cohort and scheduled time where baseline is defined to be the last non-missing assessment done prior to first dose.

For the percent change in total muscle volume at 6-months from baseline, a mixed model will be fitted using the data from Part 1 as well as the data from the double-blind component of Part 2 of studies A083-02 and A083-03 and the loading dose treatment effect will be assessed. Baseline is defined to be the last non-missing value prior to first dose of study medication. The least squares mean difference for each loading dose regimen (q4w and q3w) vs. placebo and corresponding 90% confidence interval will be provided where placebo subjects come from the double-blind component of Part 2 of A083-02 and A083-03. This will also be provided by cohort. If data from the 6-month (Day 169) visit are missing, the missing data mechanism will be investigated and an appropriate method for handling the missing data will be applied. Sensitivity analyses will also be performed.

For contractile muscle volume and intramuscular fat fraction, similar analyses as described above for total muscle volume will be provided. For biomarker data (e.g., IGF-1 and CTX), raw data and changes from baseline (percent and absolute change) will be summarized by cohort and scheduled time.

Additional analyses may be performed as appropriate.

Part 2

Individual pharmacodynamic parameter data will be listed. Descriptive statistics will be provided by cohort, treatment regimen and scheduled time for raw data and changes from baseline.

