The primary pharmacodynamic variable will be the difference in mean percent change in total muscle volume (average of left and right side) for the first 6 months of the maintenance phase (Day 169) from the total muscle volume (average of left and right sides) at the start of the maintenance phase (or equivalently the end of the loading phase). An mixed model will be fitted to the data and a non-inferiority analysis will be performed using a non-inferiority margin of -5. The non-inferiority analysis will be done for each maintenance dose regimen (q4w and q8w). The lower bound of the one-sided 95% confidence interval will be used to assess non-inferiority. If data from the 6-month (Day 169) visit are missing, the missing data mechanism will be investigated and an appropriate method for handling the missing data will be applied. Sensitivity analyses will also be performed. In addition, using the same mixed model, the percent change in total muscle volume for the first 6 months of the maintenance phase (Day 169) from the start of the maintenance phase (or equivalently the end of the loading phase) will be compared between the two dosing regimens (q8w vs q4w).

Secondary MRI pharmacodynamic variables include the difference in mean percent change for contractile muscle volume (average of left and right sides) as well intramuscular fat fraction (average of left and right sides) at the end of the first 6 months of the maintenance phase (Day 169, q4w or q8w) from the start of the maintenance phase (or equivalently the end of the loading phase). Secondary pharmacodynamic variables also include the percent and/or absolute (raw) change in biomarker variables such as CTX at the end of the first 6 months of the maintenance phase (Day 169). For each secondary MRI pharmacodynamic variable, an mixed model will be fitted to the data and least square estimates of the mean difference and corresponding 90% confidence interval will be provided for each maintenance dose regimen. If data from the 6-month (Day 169) visit are missing, the missing data mechanism will be investigated and an appropriate method for handling the missing data will be applied. Sensitivity analyses will also be performed.

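### Should entry route (Part 1 completer or direct rollover) have been a stratum in the Part 2 randomisation?

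*Protocol*

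**What the plan says.** Two places describe the Part 2 randomisation, and they agree. Section 10.5 says subjects are "grouped by disease (FSHD or CMT) and target muscle (for FSHD; BB or TA) and then randomized". Section 7.1 names the same two factors, disease and target muscle. That makes three strata: FSHD TA, FSHD BB and CMT TA.

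The synopsis (Number of Subjects) gives the sources of Part 2: "up to 54 subjects from Part 1 of this study, up to 56 subjects from Part 2 of Study A083-02", and up to 40 from Part 2 of A083-03. The Part 1 group was re-loaded with six q4w doses "after a washout period of at least 3 months" (section 7.1). The others enter without interruption from base-study Part 2, which section 5.2 describes as 12 months and 17 doses, and which had a q3w regimen and a placebo group (synopsis; section 14.2.4).

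On the analysis, section 14.2.4 states: "The non-inferiority analysis will be done for each maintenance dose regimen (q4w and q8w"). The criterion is a one-sided 95% lower bound against -5. As an addition, the Day 169 percent change "will be compared between the two dosing regimens (q8w vs q4w"). Section 14.2.4 specifies a mixed model but does not list its terms, and section 14.2 leaves further detail to the SAP.

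**The concern.** The endpoint is percent change in total muscle volume from the start of maintenance, so what a subject received before that point could bear on it. The two routes differ in dosing interval, duration, number of doses and washout. The rollovers are themselves mixed, since "placebo subjects come from the double-blind component of Part 2 of A083-02 and A083-03" and some of those subjects may have gone on to active treatment before entering here.

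Route is known at randomisation, and a stratification factor must be fixed before the list is generated. If the two arms end up with different route mixes, the q8w versus q4w comparison carries extra noise and the small by-cohort summaries become harder to read side by side. On that view a cheap safeguard was missed and could not be supplied later.

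**Working it through.** **1. The plan's own figures.** Inputs from section 14.3: SD 9, margin -5, mean -2, and a 0.05 level, which section 14.2.4 makes one-sided. The probability of passing in one regimen is Φ(3/(9/√n) − 1.645).

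- n = 75: Φ(2.887 − 1.645) = 0.893 (stated 89%)
- n = 65: Φ(2.687 − 1.645) = 0.851 (stated 85%)
- n = 57: Φ(2.517 − 1.645) = 0.808 (stated 80%)

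A two-sample calculation would give 65%, 60% and 55%. The planned test is therefore one-sample within each regimen. The route balance between arms does not enter it.

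**2. How uneven the routes can become.** From Tables 3 and 4 at full enrolment, FSHD TA has 46 subjects (18 Part 1 completers, 28 rollovers), FSHD BB has 46 (18, 28) and CMT has 58 (18, 40). The 28/28 split of the 56 A083-02 rollovers is inferred from the cohort caps. With equal arms within each stratum, the hypergeometric variance of the number of completers in one arm is:

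- each FSHD stratum: 23 × (18/46) × (28/46) × (23/45) = 2.800
- CMT: 29 × (18/58) × (40/58) × (29/57) = 3.158

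The sum is 8.758, so the SD is 2.959. The SD of the between-arm difference in share is 2 × 2.959/75 = 0.0789. The 95% range is 21 to 33 of the 54 completers in one arm.

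**3. What that does to q8w versus q4w.** With no route effect, SE = 9 × √(2/75) = 1.470. The protocol gives no route effect, so the gap g between the two route means is assumed. Chance imbalance raises the true sampling SD to √(1.470² + (0.0789g)²):

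| g (points) | sampling SD |
|---|---|
| 2 | 1.478 |
| 3 | 1.489 |
| 5 | 1.522 |
| 8 | 1.600 |

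**4. Would a route stratum repair it?** If route is not in the model, its variance stays in the residual whether or not route was balanced. Averaged over the three strata, p(1−p) is [92 × (18/46)(28/46) + 58 × (18/58)(40/58)]/150 = 0.229. For g = 5 the residual variance is 81 + 25 × 0.229 = 86.7, and the reported SE is √(86.7 × 2/75) = 1.52, with or without the stratum.

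Simulation of the three strata at full enrolment (SD 9, g = 5, disease and muscle in the model) gives this mean reported SE:

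| | no route term | route term |
|---|---|---|
| no route stratum | 1.52 | 1.47 |
| route stratum | 1.52 | 1.47 |

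To three decimals the right-hand column is 1.474 and 1.466. Once route is modelled, omitting the stratum costs about 0.5% of the SE. At g = 2 it costs about 0.2%.

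**5. Dependence on the list.** With blocks of 4 (assumed; section 10.5 does not describe the scheme), the SD of the share difference stays at 0.079 if the routes arrive interleaved. It falls to about 0.027 if they arrive in separate runs.

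**The case for a change.** The facts behind the concern are right. Route is known at randomisation, it is not a stratum, and six strata of up to 18, 28, 18, 28, 18 and 40 would be workable. A difference of 33 versus 21 completers between arms lies within the ordinary play of chance. Stratification would also reduce the true sampling variability of the q8w − q4w estimate (1.52 to 1.47 at a 5-point gap), even though an analysis without a route term would not report the gain. And no model term balances the unadjusted descriptive tables.

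None of this amounts to something stated wrongly or fixed badly. Randomisation already protects the comparison from systematic bias. The affected comparison is an addition to the main test, with no margin or power claim of its own. The protocol plans no by-route estimate, so the precision of such an estimate cannot justify the stratum. Sections 5.2 and 7.2 report that volume increases were maintained for up to 8 weeks after the last dose. Those are base-study Part 1 data, but they weigh against a large route gap.

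Two neighbouring observations do not change this. For Part 1 completers, q4w maintenance simply continues the loading interval; sections 7.2 and 14.3 declare the mixed loading openly, and no stratum would alter it. Sections 5.2 and 7.2 speak of a 6-month loading phase while 5.2 gives 12 months for base Part 2. That is a wording matter which turns on the structure of studies described elsewhere, and it changes no result.

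**Conclusion.** The concern does not hold. Stratifying on disease and target muscle is an acceptable choice for an open-label phase 2 extension, and the protocol describes it consistently. The per-regimen non-inferiority test and its 89%, 85% and 80% are unaffected.

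For the q8w versus q4w comparison, the cost of chance imbalance is small: the standard error rises from 1.47 to 1.48 at an assumed 2-point route gap and to 1.52 at 5 points. A route term in the mixed model recovers nearly all of it without the stratum. The protocol leaves the model terms open and the SAP is not at hand, so their absence here is not a defect, and it is not true that the matter can no longer be dealt with after the list is generated.

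These figures assume full enrolment, equal arms within strata, SD 9 and the stated route gaps, which the protocol does not supply.
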